10.1.7 Response Review

No external review of clinical response is planned.

10.2 Other Response Parameters

N/A

11. DATA REPORTING / REGULATORY CONSIDERATIONS

11.1 Monitoring plan

Research team will meet monthly to review the adverse events. Any severe adverse events will be reported to principal investigator immediately. The stopping rule is described below.

11.2 Stopping rules for the individual patient and for the study as a whole

Individual patient:

Patients who develop severe adverse reaction to the ATG infusion, such as serum sickness that result end-organ damage, will be removed from study.

For the study as a whole: There is no interim analysis for efficacy (PFS), but the study may stop early for safety. The safety monitoring is by means of two rules, one for Grade II-IV acute GVHD and the other for 100 day mortality. The rules call for assessing observed counts after every 5 patients and stopping as follows:

For 100 day mortality

after.pt	5	10	15	20	25	30	35	40
stop.if.reach	2	3	3	4	5	5	6	7

For Grade II-IV acute GVHD

after.pt	5	10	15	20	25	30	35	40
stop.if.reach	2	3	4	5	6	7	8	9

For example, if there are 3 deaths in the first 15 patients, the study will stop at 15 patients or earlier, or if there are 3 Grade II-IV acute GVHD cases in the first 10 patients, the study will stop at 10 or earlier, and so on. The usual 'look ahead' principle will apply: as soon as it is known that a stopping boundary will surely be reached (such as 3 deaths in the first 9 patients) the study will stop. These rules guarantee stopping if the lower 80% one-sided confidence limit for the true rate exceeds 10% for 100 day mortality or 15% for Grade II-IV acute GVHD.

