12.2 Analysis Populations

We will report outcomes on all patients who begin the preparative protocol (corresponding to the intent-to-treat principle) as the primary analysis, and also on those who actually receive transplant and those who successfully engraft (subset analyses).

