12.4 Sample Size

12.4.1 Accrual estimates

12-15 patients per year over 3 years for a maximum of 40 patients, subject to stopping rules above.

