PR	>50% regression in any splenic or liver nodules, or in measurable disease (SPD) in any organs abnormal at baseline. No increase in size of liver or spleen and no new sites of involvement.
SD	Fails to attain the criteria for CR, PR or PD
PD [*]	(1) >50% increase in size (SPD) of any organs involved at baseline or (2) New organ involvement or (3) Loss of response: in those with PR or CR, >50% increase from nadir in the size (SPD) of any previous organ involvement
Relapse	New organ involvement in those with CR

*Use of FDG-PET scan in this instance is compatible with other NHLs but there is a paucity of data in clinical trials of MF/SS to document its utility.

*Whichever criterion occurs first.

Global Response Score

Global Score*	Definition	Skin	Nodes	Blood	Viscera
CR	Complete disappearance of all clinical evidence of disease	CR			All categories have CR/NI
PR	Regression of measurable disease	CR			All categories do not have a CR/NI and no category has a PD
		PR			No category has a PD and if any other category involved at baseline, at least one has a CR or PR
SD	Failure to attain CR, PR or PD representative of all disease	PR			No category has a PD and if any other category involved at baseline, no CR or PR in any
		SD			CR/NI, PR, SD in any category and no category has a PD
PD	Progressive disease				PD in any category
Relapse	Recurrence disease in prior CR				Relapse in any category

NI = non-involved

*It is recommended that not only the proportion of patients who achieve a response or an unfavorable outcome be calculated but a life table account for the length of the interval during which each patient is under observation.

Record of Changes

Date	Protocol Changes	IRB
------	------------------	-----

		Approval Date
March 11, 2009	Original protocol	April 21, 2009
April 29, 2009	Request of the SRC for clarifications in the statistical section	May 19, 2009
June 29, 2009	Changed eligibility criteria related to prior malignancies. Clarified collection goals and processing. Changed CSA taper to begin when chimerism studies obtained. Added timeframes for chimerism evaluations. Added tumor assessments to study calendar. Updated study calendar. Added research sample calendar. Changed fasting before ECP to a low fat diet.	July 14, 2009
March 30, 2010	Decreased TLI from 1200 cGy to 800 cGy. Length of treatment and dose of TSEBT will be determined by the radiation oncologist.	April 20, 2010

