October 27, 2010	Clarified stopping rule for acute GVHD to Grade II-IV acute GVHD. Clarified minimum number of research GGT.	November 09, 2010
October 5, 2011	Modified Study calendar for BM Bx	October 18, 2011
February 24, 2012	Modified verbiage	April 17, 2012
May 31, 2012	Updated Investigators and Appendix D (response criteria)	June 19, 2102
February 28, 2013	Modified eligibility criteria 3.1.8 ALT and AST must be < 3X ULN previously </= to 3X Normal. Total bilirubin </= 2 mg/dL previously <3 unless hemolysis or Gilbert's disease. If AST and ALT are <5 x ULN, patient may be eligible if: 1 Liver biopsy performed within 60 days of HCT excludes active cirrhosis gradd greater than 2/4 and bridging fibrosis 2 No clinically evident ascites 3 Patientwith Hepatitis B or C are excluded if AST or ALT > 3 x ULN Deleted BM STR subset on section 9 of the study calendar. Deleted bone marrow biopsy on Day 90 for chimerism study in section 8.1.1.1	March 19, 2013
March 7, 2014	Changed from cyclosporine to tacrolimus Section 3 PARTCIPANT SELECTION AND ENROLLMENT PROCEDURES 3.1 Inclusion Criteria. Modified section 3.1.4 from Age > 18 years and < 75 years. to Age >18 Section 4.1.4 Immunosuppression for GVHD prophylaxis. Modified Immunosupresant from Cycloporine to Tacrolimus Section 4.3 Duration of Therapy: Day -3;Modified from Cyclosporine to Tacrolimus Section 7.ADVERSE EVENTS AND REPORTING PROCEDURES 7.1 Potential Adverse Events: Human Toxicology section: from cyclosporine to tacrolimus Pharmaceutical Data: Formulation: from cyclosporine to tacrolimus	March 18, 2014
June 13, 2014	Consent form: Modified the footer to add patient name and MRN Medical Record Number Protocol body Updated Schema Page 6 to reflect: "Length of treatment and dose of TSEBT will be determined by the radiation oncologist". Has been approved in April 10,2010 but was not change in the protocol body. Moved the "Record of Revision" from page 38 to page 42 where all the list of revisions are located. Updated the list of revisions.	June 17, 2014
November 18, 2014	Added [name] as listed personnel Protocol body: Modified section 4.1.4 Immunosuppression for GVHD prophylaxis in section n and o: Tacrolimus dose from 0.12 to 0.05 mg/kg 4.1.4 Immunosuppression for GVHD prophylaxis	June 21, 2016

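### Safety counts and final estimates run as one series from patient 1 although the regimen changed during the trial, so pooling can hide (or overstate) harm under the current version

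*Combined protocol and SAP*

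**What the plan says.** Section 11.2 gives one boundary table for 100-day mortality and one for grade II-IV acute GVHD: "The rules call for assessing observed counts after every 5 patients and stopping as follows". Both run from patient 5 to patient 40, and the examples count from the start of the trial: "if there are 3 deaths in the first 15 patients, the study will stop at 15 patients or earlier", and "if there are 3 Grade II-IV acute GVHD cases in the first 10 patients, the study will stop at 10 or earlier". The tables are said to guarantee stopping when the "lower 80% one-sided confidence limit for the true rate exceeds 10% for 100 day mortality or 15% for Grade II-IV acute GVHD". Section 12.5 repeats the rule. Neither section restarts or splits the count after a treatment change.

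Section 12.2 sets the primary analysis: "We will report outcomes on all patients who begin the preparative protocol". Its only subsets are patients transplanted and patients engrafted. Section 12 plans overall safety rates at the end of the study.

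The Record of Changes shows that patients could have been treated under different versions. The entry of March 30, 2010 reads "Decreased TLI from 1200 cGy to 800 cGy" and that of March 7, 2014 reads "Changed from cyclosporine to tacrolimus". A later entry lowers the tacrolimus starting dose. The record is used here only to establish what earlier patients may have received, not to claim a conflict with the current text.

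**The concern.** A guarantee about the true rate presumes a single rate. If TLI total or GVHD prophylaxis affects acute GVHD or early death, the series is a mixture. Event-free patients from an earlier version then raise the number of events needed among current-version patients before the rule stops. The final PFS, GVHD and mortality figures average over versions and need not describe any of them. This matters because a low GVHD rate is the stated rationale for the regimen (Sections 2.2 and 12).

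**Working it through.** **1. The printed boundaries.** The boundary at n patients is the smallest r with P(Bin(n, p0) ≥ r) < 0.20, where p0 is 0.10 for mortality and 0.15 for GVHD. This is the exact lower 80% one-sided limit exceeding p0. For mortality at n = 15, P(X ≥ 3) = 0.184 and P(X ≥ 2) = 0.451, so r = 3. For GVHD at n = 20, P(X ≥ 5) = 0.170 and P(X ≥ 4) = 0.352, so r = 5. All 16 printed values reproduce (mortality 2, 3, 3, 4, 5, 5, 6, 7; GVHD 2 to 9). The tables are computed correctly; the question is who is counted.

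**2. GVHD, without assuming any rates.** The boundary is n/5 + 1. After k earlier patients (k a multiple of 5) with c cases, stopping at j current-version patients needs (k + j)/5 + 1 − c cases. A restarted table needs j/5 + 1. The difference is k/5 − c. A trial still open has c ≤ k/5, so the difference is never negative. The pooled GVHD rule is therefore never more sensitive than a restarted one, and is less sensitive whenever c < k/5. With no cases in the first 15, pooling needs 5 of 5, 6 of 10 or 7 of 15; a restart needs 2 of 5, 3 of 10 or 4 of 15.

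**3. Mortality.** The direction can go either way. With no deaths in the first 20, pooling needs 5 of the next 5 or 5 of the next 10 (restart: 2 or 3). With 2 deaths in the first 10, a single death in the next 5 stops the trial (restart: 2 of 5).

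**4. Chance of stopping by patient 40.** This is an exact binomial recursion over the looks at 5, 10, ..., 40, conditional on not having stopped by patient k. The look-ahead clause brings a stop forward but does not change its probability. The assumptions are:
- k is not given in the documents, so a range is shown.
- The earlier GVHD rate is 4% (the acute GVHD figure in Section 2.2) to 15% (the rule's own threshold).
- The later rate is 30%, twice the GVHD threshold.
- Earlier mortality is also taken as 4%.

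| Earlier patients k | GVHD pooled, earlier 4% | GVHD pooled, earlier 15% | GVHD restarted | Mortality pooled, 4% then 30% | Mortality restarted |
|---|---|---|---|---|---|
| 10 | 68% | 78% | 91% | 91% | 98% |
| 20 | 23% | 49% | 84% | 57% | 93% |
| 25 | 7% | 33% | 78% | 31% | 88% |

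**5. The pooled estimate.** With 15 patients at 5% and 25 at 30%, the expected pooled rate is (15 × 0.05 + 25 × 0.30)/40 = 8.25/40 = 20.6%, which understates the current version. Reversed, (15 × 0.30 + 25 × 0.05)/40 = 5.75/40 = 14.4%, which overstates it.

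**6. False-stop cost of a second count.** Same recursion, with one rate throughout that lies below the threshold. Under the added rule either count stops the trial; for GVHD this equals a restart, by step 2.

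| True rate | k | As written | With added count |
|---|---|---|---|
| GVHD 10% | 10 | 4% | 15% |
| GVHD 10% | 20 | 1% | 14% |
| Mortality 8% | 10 | 12% | 21% |
| Mortality 8% | 20 | 4% | 15% |

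For scale, the printed GVHD table applied from patient 1 over 40 patients stops 15% of the time at a true rate of 10%.

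**The case against.** The strongest reply is that a reader might infer that earlier patients are in fact masking harm, or that the rule has little power left after the prophylaxis change. The documents support neither. They report no higher event rate under the current version and do not say how many patients preceded each change. With only 5 earlier patients at 5%, the GVHD rule still stops 85% of the time, against 93% restarted. At the planned accrual ("12-15 patients per year over 3 years for a maximum of 40 patients, subject to stopping rules above"), about 12-15 patients would precede the April 2010 approval of the TLI change. The same plan would have all 40 enrolled before the 2014 change, but the record runs to 2019, so actual accrual is unknown.

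The 4% anchor is also weak. It is an acute GVHD rate with no grade stated, from the centre's wider series rather than this trial, and the 30% is an assumption. This stands, and is why an earlier rate of 15% is shown alongside; a material loss remains at 20 or more earlier patients.

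A reader might also think that a parallel stopping count is nearly free because the added false-stop risk is small at a true rate of 4%. At rates closer to the thresholds but still acceptable it adds about 9 to 13 percentage points (step 6). A mandatory second count is therefore a trade-off, not a wording change.

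Finally, the team reviews adverse events monthly (Section 11.1), and Section 12.5 allows stopping for safety at any time. That is partial mitigation only, since Section 12.5 then specifies the same five-patient rule.

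**Conclusion.** The concern holds as a possibility, not as a demonstrated harm. The plan pools counts and estimates across treatment versions and provides no view by version. For GVHD, pooling can only reduce the rule's sensitivity to the current version. For mortality the loss is smaller at the same earlier numbers, and the direction can reverse. The size depends on the number of earlier patients, which is not given: under the stated assumptions, GVHD detection falls by 13-23 percentage points with 10 earlier patients (91% to 78% or 68%) and by 35-61 points with 20 (84% to 49% or 23%). Final estimates can err in either direction. Reporting by version is a clear, inexpensive improvement; a formal restart is a choice for the sponsor to make with its cost in view.

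**What to change.** - **Sections 12.2 and 12.3.** Add: *180-day PFS, grade II-IV acute GVHD and 100-day mortality will be reported by regimen version (TLI total received, calcineurin inhibitor) with exact 95% intervals, beside the pooled result; the safety conclusion will be drawn with the current-version figures shown.* The cost is one tabulation and wider intervals: at 75% PFS, the exact interval is 51% to 91% for 15 of 20, against 58% to 88% for the protocol's example of 27 of 36.
- **Section 11.2.** Show the event counts by version at each five-patient look, beside the cumulative count. This changes no boundary.
- **Optional, Section 11.2.** If a restarted or parallel count is adopted, define which treatment change triggers it and state its operating characteristics as in step 6. Each further restart adds false-stop risk.
- **Identifiability.** The synopsis gives a TLI total of 800 cGy. Section 4.1.2 gives ten fractions of 80 to 120 cGy, that is 10 × 80 = 800 to 10 × 120 = 1200 cGy. These passages must be reconciled so that a patient's regimen version can be identified.

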11.3 Data management

All the clinical data from this study will be maintained by BMT data management team.

11.4 Confidentiality

All patients undergoing hematopoietic cell transplantation at Stanford are assigned a SPN (Stanford Patient Number) and data is entered into a secure database. Access to the database is limited to study personnel and password protected. Research records are maintained in a secure office of the data management staff.

12. STATISTICAL CONSIDERATIONS

The primary goal of this study is to provide proof-of-concept evidence for the safety and efficacy of non-myeloablative allogeneic transplant with TLI/ATG conditioning for patients with MF/SS as described above. Safety will be measured at the end of study by rates of GVHD, other measures of side effects, and overall survival (see above for safety monitoring methods). The primary efficacy endpoint is PFS at 180 days. The historical control for safety is the acute GVHD and mortality rates of myeloablative allogeneic treatment. The rationale for this study is based on the expectation that the new non-myeloablative allogeneic transplant will achieve response rates (and subsequent disease control) that is comparable to myeloablative allogeneic transplant, but with a great reduction in GVHD and TRM.

12.1 Endpoints

12.1.1 Primary endpoint

The primary efficacy endpoint is PFS at 180 days (defined above). The safety endpoints include GVHD and other treatment related events, including mortality.

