4.1.6 Engraftment and Disease Status Monitoring

- s) Patients will be followed in the ITA for signs of infection or GVHD. Monitoring for engraftment and infection will be according to current standard of care of Stanford BMT program.
- t) Chimerism: Microsatellite analysis (VNTR) of CD3, CD19, CD15, and CD56 peripheral blood cell subsets will be performed on days +28 (\pm 5 days), +56 (\pm 5 days), +90 (\pm 14 days), +180 (\pm 14 days), +270 (\pm 14 days), and yearly (\pm 4 weeks) to evaluate the degree of donor hematopoietic cell engraftment (donor chimerism), and on bone marrow on day +90 (\pm 14 days), and yearly per physician's discretion.
- u) Clinical response will be determined at 3, 6, 9, 12, 18, 24 months or until relapse or progression after transplant. The disease status and clinical response will be scored on a rigorous and multifactorial approach described before (41, appendix). This approach takes tumor burden in skin, lymph nodes and blood into consideration. To achieve this, patients will be evaluated at Cutaneous Lymphoma Clinic before transplant and at specified time points after transplant.

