9. STUDY CALENDAR

	BS	Post-Transplant Day							
		±5 days	±5 days	±10 days	± 2 wks	± 2 wks	± 2 wks	± 4 wks	± 4 wks
		d+30	d+60	d+90	d+180	d+270	d+365	d+540	d+730
Informed Consent	X								
Path Review	X								
H&P/KPS	X								
PFT	X								
Echo	X								
CBC with diff	X								
Chemistry: BMT I	X								
HLA confirmed	X								
BMT Panel (serologies)	X								
CXR	X								
EKG	X								
STR subsets: PB		X	X	X	X	X	X**		X
BM bx/asp**	X			X			X		X
Research Samples		X	X	X	X				
Skin Biopsy	X			X					
Flowcytometry** (SS only)		X		X	X	X	X	X	X
Disease Status/Response**	X			X		X	X	X	X
GVHD assessment	X	X	X	X	X	X	X		X

** Per Attending Physician's discretion

Correlative Study Calendar

	Donor Chimerism	Chemokine Receptor Profile	Th1/Th2 Phenotype	Treg Cell Quantity	Treg Cell Function	Skin Biopsy Pathology	Skin Biopsy T Cell Trafficking	Derm Clinical Assessment	Bone Marrow Biopsy	CTL Assay	Tumor Cell Banking
Pre TSEBT		X		X		X		X	X	X	Sezary only
Pre TLI/ATG		X		X		X	First 5 pt	X			
Pre Infusion		X		X							
+ 30 day	X	X	X	X	First 5 pt			X			
+ 60 day	X	X	X	X				X			
+ 90 day	X	X	X	X	First 5 pt	X	First 5 pt	X	X	X	
+ 180 day	X	X	X	X	First 5 pt		First 5 pt	X	X	X	
+ 270 day	X	X	X	X				X			
+ 1 year	X	X	X	X	First 5 pt		First 5 pt	X	X	X	
+ 2 year	X							X	X		
Cell Product		X	X	X							
Pre ECP		X	X	X							
Post ECP		X	X	X							
Disease Regression						X		X			
Disease Progression						X		X			
Sample		Up to 5 GGT			5 mm punch	5 mm punch		Routine	2 GTT for effector	2 GTT	
Site	HLA Lab	HIMC	CTF	CTF	CTF	Path	CTF	Cut Lym Clinic		HIMC	HIMC
Assay	Chimerism: CD3, CD19, CD56, CD15	Skin: CCR4, CCR10, CLA; LN: CCR7	Th1: IL-2, IFN γ ; Th2: IL-4, IL-10	FoxP3 positive	Inhibition of MLR	Monitoring Residual Disease	Lymphocyte Donor Chimerism, Chemokine receptor		FAM-VAD Assay	Use as Target Cell for CTL	

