10.1 Anti-tumor Effect

10.1.1 Definitions

Disease status will be evaluated right before non-myeloablative allogeneic transplants and at 3, 6, 9, 12, 18, 24 months after allogeneic transplant or up to 1st recurrence or progression.

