10.1.6 Progression-Free Survival (or other parameters)

Event-free survival (EFS) is the time measurement between the day of allogeneic transplant and the first documented recurrence or death from any cause. Overall survival (OS) is the time measurement between the day of allogeneic transplant and death from any cause.

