12.3.2 Evaluation of Efficacy

Efficacy will be evaluated by calculating the Kaplan-Meier estimates of progression-free survival (PFS, i.e., probability of remaining alive and free of progression). We will also calculate the cumulative incidence estimate of the progression rate, using non-relapse mortality as a competing risk.

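### A progression first documented at a 6-month assessment on days 181 to 194 counts as progression-free at day 180, so the primary PFS figure leans upward by an amount that depends on clinic booking

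*Combined protocol and SAP*

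**What the plan says.** Section 12.1.1 sets the time point: "The primary efficacy endpoint is PFS at 180 days (defined above". Section 12.3.2 sets the estimator: "Efficacy will be evaluated by calculating the Kaplan-Meier estimates of progression-free survival".

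PFS has no dating rule of its own. Section 10.1.6, headed as progression-free survival, defines EFS as the time between "the day of allogeneic transplant and the first documented recurrence or death from any cause". Applying that text to PFS is the natural reading, but it is an inference.

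The assessment schedule appears in three places:

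- Section 4.1.6(u): "Clinical response will be determined at 3, 6, 9, 12, 18, 24 months or until relapse or progression after transplant". No window is given.
- Section 10.1.1: disease status is evaluated before transplant and "at 3, 6, 9, 12, 18, 24 months after allogeneic transplant or up to 1st recurrence or progression". No window is given.
- Section 9: the d+180 column has a window of plus or minus 2 weeks. The row "Disease Status/Response" is marked at baseline, d+90, d+270, d+365, d+540 and d+730. Its d+180 cell is blank, and a footnote leaves the row to the attending physician's discretion.

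No section assigns an assessment inside the window to the 180-day time point, or says how to treat one that falls after day 180.

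**The concern.** A Kaplan-Meier estimate at day 180 is not lowered by an event dated day 181 or later. A patient who progresses on day 150 and is first found to have progressed on day 185 is progression-free in the primary estimate. A patient with the same course seen on day 178 is a failure.

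The error runs one way. Progression cannot be documented before it happens, and an early visit does not offset a late one: a patient who is clear on day 170 and progresses on day 175 may not be documented until the next visit, and also counts as a success. With no control arm, nothing cancels the shift. Section 12.4.2 reads the result against a 75% target and calls a value substantially closer to 50% not encouraging, so an upward shift favours the treatment.

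**Working it through.** **Inputs from the plan.** Time point day 180, Kaplan-Meier (12.1.1, 12.3.2). Event at first documentation (10.1.6). Windows of 90 ± 10, 180 ± 14 and 270 ± 14 days (Section 9). Target 75%, 95% half-width 15%, example 27/36 (12.4.2).

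**Assumptions.** The plan gives no visit-timing or hazard data. I take a constant hazard with true S(180) = 0.75, so λ = −ln(0.75)/180 = 0.0016 per day. The 3-month visit is even over day 80 to 100. Progressions are dated at the visit that detects them and deaths on their own day. There is no off-schedule documentation.

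**Step 1: the plan's own figure.** The exact binomial interval for 27/36 is 57.8% to 87.9%, half-width 15.0%. For 18/36 the half-width is 17.1%. Both agree with 12.4.2. The issue here is bias in the estimate, not the width of the interval.

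**Step 2: share of 6-month visits after day 180 (q).**

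- Even over day 166 to 194: (194 − 180)/28 = 50%, or 14/29 = 48.3% in whole days.
- Centred on six calendar months, 365.25/2 = 182.6 days: (196.6 − 180)/28 = 59%. Centred on day 183 in whole days: 17/29 = 58.6%.
- Booked early (normal, SD 5 days, cut to day 166 to 194): 35%, 22% or 9% for centres at day 178, 176 or 173.

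**Step 3: measured PFS.** If all events are progressions, a patient counts as progression-free at day 180 in one of two ways: assessed by day 180 and clear then, or assessed later and clear at the 3-month visit. So

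measured = (1 − q) × mean S at visits by day 180 + q × mean S at the 3-month visit,

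where the last mean is 0.866. If half of events are deaths, which keep their own dates, measured = 0.5 × 0.75 + 0.5 × the all-progression figure.

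| 6-month visit | q | Mean S, visits by day 180 | All progressions | Half deaths |
|---|---|---|---|---|
| Even, centre 180 | 0.483 | 0.758 | 0.517 × 0.758 + 0.483 × 0.866 = 0.810 | 0.780 |
| Even, centre 183 | 0.586 | 0.757 | 0.414 × 0.757 + 0.586 × 0.866 = 0.821 | 0.785 |
| Early, centre 178 | 0.347 | 0.756 | 0.653 × 0.756 + 0.347 × 0.866 = 0.794 | 0.772 |
| Early, centre 176 | 0.217 | 0.757 | 0.783 × 0.757 + 0.217 × 0.866 = 0.781 | 0.765 |
| Early, centre 173 | 0.088 | 0.759 | 0.912 × 0.759 + 0.088 × 0.866 = 0.768 | 0.759 |
| Window day 166 to 180 | 0 | 0.758 | 0.758 | 0.754 |
| No d+180 assessment | 1 | none | 0.866 | 0.808 |

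Simulation of the same set-up gives the same figures to within rounding. Every row lies above the true 0.75, and the window ending at day 180 comes closest.

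**Step 4: price of the dating rule.** Counting progressions found up to day 194 as events by day 180 also takes in some that began after day 180. That is at most S(180) − S(194) = 0.750 − 0.733 = 1.7 points, reached only if every assessment fell on day 194.

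**The case against.** **The two-week window is not attached to this assessment.** Sections 4.1.6(u) and 10.1.1 give 6 months without a window, and the calendar column that has one carries no disease-status mark. This stands as a contradiction to be reconciled, and the blank cell should be confirmed against the formatted table. It does not remove the problem. Section 4.1.7(w) schedules Sezary-cell flow cytometry at the same months as clinical response, and the calendar marks that test in the d+180 column, which ties 6 months to that column. If the blank cell is followed instead, the bias is larger.

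**Progression may be documented off schedule.** The correlative calendar has an event-triggered row for disease progression, Section 8.1.3.1 takes a biopsy at progression, and skin disease is visible. This stands: such progressions keep their earlier dates and reduce the bias. The table assumes none, so it shows the upper side for each visit pattern. The correlative calendar's scheduled dermatology assessments add no visit between +90 and +180 days.

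**The convention is ordinary and the study is modest.** Dating progression at documentation is common practice. This is a single-arm proof-of-concept study with no hypothesis test, and the plan does not say how its 75% target was derived or dated. That limits the severity. It does not justify leaving the primary figure to depend on booking when a wording change would prevent it.

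**A tempting stronger reading.** A reader might infer that half or more of the progressions found at this visit necessarily escape. The documents do not support that. It needs visits centred on day 180 or later; with early booking the share of visits after day 180 is roughly 10 to 35%. Nor do they say how many patients will have progression first found at this visit, so a bias in patient counts cannot be read from them.

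**Conclusion.** The point holds in a limited form. As written, a progression first documented at the 6-month assessment on days 181 to 194 is a success in the primary estimate, and no rule prevents this. Deaths, and progressions documented earlier, are unaffected.

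Assuming constant hazard, true PFS of 75% and no off-schedule detection, the upward bias is about 6 to 7 points if visits spread evenly around day 180 to 183 and all events are progressions. It is about 3 points if half are deaths, and about 1 to 4 points with early booking. With no d+180 assessment it is about 6 to 12 points. None of these is a figure from the plan.

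Because six calendar months already lies past day 180, a reader might also infer that every progression found at this visit is lost. That would require every patient to attend on or after day 181, which no section states. Nor does the point undermine the precision statement in 12.4.2, which reproduces. I class it as a cheap improvement.

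**What to change.** - **Section 9:** reconcile the calendar with 4.1.6(u) and 10.1.1 by marking the disease assessment at d+180. For that assessment only, set the window to day 166 to day 180.
- **Sections 4.1.6(u) and 10.1.1:** give the same window for the 6-month assessment.
- **Section 12.3.2:** state that progression first found at a late 6-month assessment, up to day 194, counts as an event by day 180, while deaths and off-schedule progressions keep their own dates.

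Reading the Kaplan-Meier curve at day 194 could serve as an alternative or a sensitivity analysis. It is not equivalent, because it also counts deaths and unscheduled progressions on days 181 to 194 and so changes what is estimated.

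Under the assumptions above, the window ending at day 180 brings the measured figure to about 75 to 76% when the truth is 75%. The cost is wording in four sections and slightly tighter booking of an assessment the text already schedules. The reported PFS may be lower, and a few progressions that began on days 181 to 194 will count as events.
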